#### 12.3 Certificate of Confidentiality

As an additional level of safeguard for study participants, we have obtained a Certificate of Confidentiality from the NIH. Having this Certificate means that investigators and study personnel cannot be forced to disclose research information that might identify the subject in any federal, state, or local criminal, civil, administrative, legislative, or other proceedings. This is important because TBI patients are often involved in high-risk behaviors that result in their injuries.

## 12.4 Potential Benefits of Proposed Research

There is no direct benefit to study participants. The results will be directly relevant to society in general and to future patients who suffer TBI. Tokens of thanks for study participants are especially important in longitudinal studies, where the burden on the respondent, even if small, tends to multiply over time. Each site will establish a reimbursement schedule for each of the time-consuming components of the study, including travel, MRI, telephone and in-person outcomes testing.

TRACK-TBI subjects will undergo extensive neuropsychological testing and brain imaging. These procedures are not part of the standard of care for mild TBI.

All subjects will have access to the results of their research MRI results within 2 weeks of the MRI
collection. If requested, subjects will receive a CD of their conventional MR imaging data and a viewer
application tool. The Patient Number will be stripped from the MRI scan.

For details regarding the release of outcomes testing results to the participants refer to the section '10 Protocol for Sharing Outcome Data with Participants'.

#### 13 SUBJECT COMPLIANCE AND RETENTION

We will monitor subject compliance with the observational portion of the protocol, and research personnel will maintain scheduled contact with the subjects and their family members to ensure on-going compliance through the 3-month study duration. Upon consent and enrollment, participants will be asked to provide multiple forms of contact information including phone, address, and email. Upon their permission, participants will be asked to provide one or more alternate contacts. The Site will maintain a schedule of contacts to maximize the chance of successful communication and scheduling for follow-up time points as soon as their window of return opens for that time point. This will involve training Research Coordinators to monitor their own site progress, which will be supplemented by automated reminders of upcoming windows for follow-up generated by QuesGen Systems and emailed to each site coordinator weekly. Every effort will be made to schedule return visits at the subject's convenience, and multiple procedures for that time point will be scheduled on the same day. When subjects return for their follow-up, they will be met by research personnel who will escort them to the various testing locations. Subjects will have full opportunity to ask any questions before, during, and at the end of the follow-up appointment. Site Coordinators will be encouraged to have relevant resource packets and materials for TBI assembled to provide to study patients.

In the event that a participant misses a follow-up time point, every effort should be made to schedule subsequent visits for outcome assessment, neuroimaging, and blood draws.

• If an in-person assessment cannot be scheduled despite multiple attempts, outcome assessments at that time point should be collected by phone.

#### 14 DATA MANAGEMENT AND COMPLIANCE

#### 14.1 Clinical database

Upon study enrollment, the subject will be entered onto the QuesGen System, which will automatically generate a Patient Number. This Patient Number is not generated from personally identifiable information (PII). Patient Numbers in this study will be assigned as follows: each site will start with subject "PM-XX-3001" for the Patient Number where PM = Study Name, XX = Site ID (see Site IDs for the 5 participating study sites below), and the last four digits will start at "3001" and increase consecutively with each enrollment at the site. MRI scans will have an additional label at the end to distinguish the time point and whether the scan is a patient or phantom. The additional labels are as follows: (PM-XX-XXXX\_Ultra-early for MRI within 48 hours, \_2WK for 2-week MRI, \_3MO for 3-month MRI and \_PHA for phantom). Clinical data will be entered into eCRFs via a web-based portal to the secure, fully HIPAA-compliant QuesGen clinical database.

## Site IDs for participating sites are as follows:

Site Name	Site IDs
UCSF	03
Univ. of Pittsburgh	07
Univ. Pennsylvania	12
MCW	14
Univ. of Utah	15

**Automated data integrity monitoring.** All clinical data will be entered into electronic Case Report Forms (eCRFs) and managed by the QuesGen data management platform. As data is entered into each form, the system will run data validation checks that include conditionally required data, validation across fields, and validation requirements based on subject type. If any validation check fails, the user is alerted immediately that the data does not meet QA criteria and the issue can be addressed and corrected at that point. If a data

element fails a validation check, yet the value entered is correct, the user can enter an exception to the problem and provide a notation as to why the out-of-range data is actually correct.

- **Date/time value checks:** all dates and times entered into the database are checked to ensure that events recorded are accurate and in sequence.
- Range value checks: all numeric, non-date fields have range values specified to minimize data entry errors.
- **Selection lists:** all categorical data fields have predetermined drop-down lists, check boxes, or resettable radio buttons instead of free text to ensure accuracy.
- Logic checks: data fields from different sections of the eCRF will be compared to pass logical integrity
- **Required fields:** the eCRF will be programmed to require input into fields when appropriate to minimize missing information.
- Score calculation will be performed and programmed into eCRFs for tests and measures with numerical score summations or norming to avoid mathematical errors by the examiner. All automated scoring computations will be fully documented and validated by QuesGen and the Clinical Core, and must pass User Acceptance Testing.
- **Electronic data audits** will be automated in the QuesGen database through a series of pre-determined queries against the study database at regular intervals. These queries will be designed for the Clinical Core to monitor data quality and completeness and identify protocol variations/deviations/violations.
- Data audits against source documents, where available, will be conducted prior to the final "lock" of each subject's data set. Errors found will be corrected at this time.

All investigators and designated study personnel will have unique and confidential password access to the QuesGen database. All access to the database and to study data will be logged in an audit trail and monitored. Any indication of inappropriate access will be reported immediately to the Clinical Core.

The QuesGen system will also provide checks for form completion based on the subject type. Validation rules will establish when forms for a particular subject should be entered, and any missing forms can be tracked by the Study Site and Clinical Core immediate follow-up. Once subject forms are marked complete, a dataset for sharing can be created. The QuesGen platform stores the exact dataset that is shared for future reference.

Due dates for eCRF completion windows are set by the Clinical Core. The Subject and Presentation eCRFs need to be initiated as soon as possible following enrollment in order to assign subject IDs for the biospecimen vials. In general, every effort should be made to complete eCRFs within 2 business days of enrollments, inpatient stays, follow-up milestones and discharges. It is understood that some forms and fields within forms may not yet have complete information available to report (e.g., Hospital Admission/Discharge, AIS/ISS, Surgeries, Concomitant Medications, etc.). The QuesGen System will automatically generate reminders to complete eCRFs for enrolled patients. Monthly reports of enrollment, timeliness of eCRF completion and error correction will be monitored and adjudicated by the Clinical Core.

**Integration with analytics platforms.** All de-identified electronic study data in the TRACK-TBI database will be maintained in secure storage by QuesGen Systems for the duration of subject enrollment and follow-up and for a period afterwards for data analysis and preparation of publications. We estimate that the analysis and publication period will last for several years after the conclusion of subject enrollment.

Together with QuesGen Systems, the Clinical Core will ensure that data standards are established for the data model e.g., conformity of field formats, field codes and names to ensure consistency across all datasets. After the initial approval of the data model and eCRFs, any proposed changes to the database will be reviewed by QuesGen and the Clinical Core for impact upon the existing data in the repository. Approved changes will be fully documented with dataset updates to maintain data quality and accuracy.

# 14.2 Biospecimens (See Appendix 2: TRACK-TBI Precision Medicine Biospecimen MOP for detailed biospecimen procedures)

Biospecimens collection. Study sites will collect, process, and ship blood and CSF (if collected) biospecimens according to the NINDS TBI-CDE Biospecimens Protocol, to a central biorepository at University of Pittsburgh. Each site will batch and ship biospecimens to the central repository on a quarterly basis. Formalized QC/QA policies for collection, processing and storage were developed and validated for TRACK-TBI Pilot. Refer to Appendix 2: TRACK-Precision Medicine\_Biospecimen Protocol\_MOP\_v1.5\_APR062021 (also saved on the Study Shared Box folder at: TRACK-TBI Precision Medicine Study Documents\Biospecimens Core\ Biospecimens MOP) for detailed information regarding management of collection supplies (disposables and reagents), identification (using Patient Number), labeling conventions, collection and processing methods, storage and retrieval, shipping and receiving, training, and security. Together these pre-analytic QC/QA policies minimize circumstances that could adversely affect scientific results, ensure the safety of research personnel, and aid in the efficient operation of the TRACK-TBI Biospecimen Core. The Biospecimen Core will review the efficiency of existing processes and procedures on a quarterly basis.

Biospecimen Repository. The NTBI-BR at the University of Pittsburgh will manage receiving biospecimen shipments from all participating sites, inventory of those shipments, storage of all study biospecimens, and shipment of study biospecimens to relevant analytic partners, where genomic and proteomic analyses will be used to discover new TBI biomarkers. See Appendix 2: TRACK-Precision Medicine\_Biospecimen Protocol\_MOP\_v1.5\_APR062021 for more details (also saved on the Study Shared BOX folder at: Box\TRACK-TBI Precision Medicine Study Documents\Biospecimens Core\ Biospecimens MOP)

# 14.3 Neuroimaging (See Appendix 1: TRACK-TBI Precision Medicine Neuroimaging MOP for detailed neuroimaging procedures)

Standardization of MR across sites. All study MR systems will initially be characterized with the Magphan® Quantitative Imaging Phantom (Phantom Laboratory, Salem, NY) designed to measure signal-to-noise ratio, object size scaling, and spatial distortion. The Magphan® Phantom has been extensively used for high-resolution structural brain imaging in numerous trials, including ADNI, as follows:

- 1. Serial imaging of the phantom will track scanner performance over the study enrollment period using an online MR Distortion and Image Quality service (ImageOwl, Salem, NY) which identifies scanner errors or defects and corrects for scaling errors and gradient non-linearity.
- 2. Standardization for diffusion MR imaging using an ice water phantom adopted by ACRIN for multi-site diffusion imaging trials.
- 3. Performance of fMRI will be assessed using the Biomedical Informatics Research Network (BIRN) phantom, with serial data analyzed to assess signal mean and standard deviations, temporal fluctuations, and drift.

Standardized MR protocols will maximize consistency among study sites and across vendor platforms. Within vendors the protocols will be identical and shared via manufacturer-generated tools (e.g. edx files, examcards). Across vendors, protocols will match spatial coverage, voxel dimensions, and primary contrast parameters (e.g. echo time, repetition time). A TRACK-TBI board-certified neuroradiologist will evaluate the test-retest scans from all sites to assure diagnostic image quality and for pathoanatomic analysis of structural MRI sequences.

Neuroimaging Repository. All study neuroimages (CT and MRI) will be de-identified at each study site before uploading to the TRACK-TBI neuroimaging core repository (Flywheel) as DICOM files, utilizing the Neuroimaging Core's de-identification and transport protocol. Image data will then be passed into one of a series of modality-specific semi-automated quality assessment pipelines and evaluated by the Neuroimaging Core for protocol conformance and quality. QA results will be provided to acquisition sites within 48 hours and

the scan repeated if it does not meet QA criteria. Images passing QA will be sent into a modality-specific image analysis pipeline and the resulting processed images and measures will be returned to the neuroimaging repository. The existing image processing provenance collection method will ensure that derived images and data are properly annotated and preserved for future research.

Integration and analysis. The Neuroimaging Core will direct the coding of all TRACK-TBI neuroimages. Final versions of the curated TBI-CDE compliant clinical and outcomes data, neuroimaging, and molecular measures will be integrated within Flywheel. Analytic systems within Flywheel will support real-time inspection of data, hypothesis testing, data subsetting, and data exploration across studies.

See TRACK TBI Precision Medicine Neuroimaging MOP V3\_TRACK-TBI\_MRI\_Manual\_27JULY2018 for more details (also saved on the Study Shared BOX folder at: Box\TRACK-TBI Precision Medicine Study Documents\Neuroimaging Core\ Neuroimaging MOP)

#### **15 ADVERSE EVENTS**

Events may be categorized as Adverse Events (AEs) if the distress felt by the subject requires termination of testing or procedure (e.g., outcomes testing, MRI). Anticipated AEs in TRACK-TBI include:

- Excessive discomfort, pain, or bruising during venipuncture
- Claustrophobia or severe anxiety in the MRI
- Anxiety during outcomes battery administration due to sensitivity of material discussed
- Anxiety due to fear of legal discovery associated with high-risk/illegal behaviors during interview

**15.1 Reporting Procedures.** AEs will be documented in the AE section of the QuesGen database. Each Site PI will be informed on a weekly basis regarding the number and nature of the AEs at their site. The Clinical Core will review the number and nature of AEs at each site on a monthly basis. Given that each site must reach the 80% completion of follow-up milestones, if AEs exceed 10% of site enrollment the Clinical Core will contact the site to discuss potential methods for reduction of AE incidence.

**15.2 Other Serious Events.** Any other serious events that do not meet the above criteria will be reported to the Clinical Core within five working days. These AEs will be recorded for individual subjects during the 3-month study period. In addition to submission as required per IRB regulations, AE data will be analyzed quarterly and reported in the quarterly reports submitted to the Executive Committee.

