## 6.9 Single Institutional Review Board (sIRB) and Human Research Protections Office

As of January 2020, all federally-funded studies are now required to use a Single Institutional Review Board (sIRB). UCSF will serve as the sIRB for this TRACK-TBI Precision Medicine protocol. Participating sites will rely on UCSF as the IRB of Record for this protocol. The UCSF Lead Coordinating Site Study Team is responsible for securing initial IRB approval from UCSF for this MSP (Master Study Protocol) and all other study documents such as the Informed Consent Form, any recruitment materials, and all study Standard Operating Procedures (SOPs) that describe the procedures and operations of the study as they pertain to enrolled subjects. Other sites cannot be added to the protocol until UCSF has initial approval for the study. The UCSF Lead Coordinating Site Study Team will utilize the online SMART IRB system to request, track, and document reliance on UCSF IRB for each Relying Site under the SMART IRB Agreement.

All relying sites' Study Teams will use the Informed Consent Form template(s) provided by the UCSF Lead Coordinating Site Study Team. Site Study Teams will provide any site-specific informed consent form language required for local study team contact details, compensation for injury, study participant reimbursement, etc. The Site Study Team will incorporate these site-specific changes to the Informed Consent with tracked changes, and will provide this form to the UCSF Lead Coordinating Site Study Team for submission to UCSF IRB.

The UCSF Lead Coordinating Site Study Team will be responsible for submitting amendments to the MSP as well as any unanticipated events, protocol deviations, adverse events, and annual continuing reviews, in accordance with UCSF IRB's established procedures and policies. The UCSF Lead Coordinating Site Study Team and participating relying Site Study Teams will follow the procedures as set forth in the UCSF sIRB Standard Operations Procedures (See "sIRB SOP for sites v2.2" on the Study Shared BOX folder at "Box\TRACK-TBI Precision Medicine Study Documents\Regulatory\IRB\sIRB SOP for all sites).

After IRB approval is obtained, the approved master study protocol (MSP) and supporting documents will be submitted to the Department of Defense Human Research Protection Office for review. Human subjects research cannot begin at a site until HRPO approval has been obtained.

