#### Outcomes

- MRI and Outcomes not completed within 3 days of each other
- Certain outcome measures incomplete
- Certain outcomes measures missed
- Other:

In most instances and especially concerning enrollment, MRI, or outcomes administration dates, protocol deviations must be reported to the Executive Committee for approval before data collection can resume for the subject at the respective time point of deviation. Due to the time sensitivity of blood draws and processing, deviations can proceed at the local level, but must be reported to the Clinical Core within 2 business days. Under circumstances in which the permissible window for outcome assessment cannot be met, with agreement from the subject, data collectors can request permission from the Executive Committee to complete the scheduled follow-up out-of-window. A protocol deviation will need to be reported within the QuesGen database, even if permission is obtained in advance.

In the event that a consistent pattern of poor performance (e.g., not enrolling allotted amount of patients per month, not achieving at or above 80% follow-up rate across all time points) or inadequate compliance (e.g., insufficient blood draw amount, CT or MR imaging, CRF completion without errors, full outcomes battery completion, or any time point completed outside the approved window) is detected, the responsible site investigator will be notified and required to present a plan for improvement and a time line for accomplishing this to the Clinical Core. Failure to meet objectives specified in this plan may result in termination of the project or assignment of the project to another investigator.

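### Section 15.2 limits the five-working-day report to serious events outside the AE criterion, so a serious event in which distress ends a study procedure has no individual reporting deadline to the Clinical Core

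*Protocol*

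**What the plan says.** Section 15 of the protocol gives one test for an adverse event: "Events may be categorized as Adverse Events (AEs) if the distress felt by the subject requires termination of testing or procedure". Four anticipated examples follow: problems at venipuncture, claustrophobia or severe anxiety in the scanner, and two kinds of anxiety during assessment or interview. How serious the event is does not enter the test.

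Section 15.1 sets the route for AEs. They are entered in QuesGen; "Each Site PI will be informed on a weekly basis regarding the number and nature of the AEs at their site"; and "The Clinical Core will review the number and nature of AEs at each site on a monthly basis". There is no separate branch for an AE that is also serious.

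Section 15.2, headed as covering other serious events, provides: "Any other serious events that do not meet the above criteria will be reported to the Clinical Core within five working days". It then refers to those same events as AEs, although it has just described them as falling outside the AE criteria. It continues: "In addition to submission as required per IRB regulations, AE data will be analyzed quarterly", with quarterly reporting to the Executive Committee.

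Section 6.9 makes the lead coordinating site responsible for submitting to the single IRB "any unanticipated events, protocol deviations, adverse events, and annual continuing reviews, in accordance with UCSF IRB's established procedures and policies". The protocol states no deadline for this.

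**The concern.** The only individual, time-limited report of a serious event to the Clinical Core is tied to an exclusion. To qualify, the event must be serious and must also fail the AE criterion. An event that is serious and meets the criterion is left to a cycle that appears designed for tolerability complaints: a weekly summary to the Site PI and a monthly count-and-nature review by the Clinical Core.

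The combination can occur. Section 15 itself anticipates anxiety during the outcome battery. Section 9.4 foresees moderate- or high-risk answers on the suicide screen. If a participant in crisis cannot continue and the session ends, the AE criterion is met. Severe distress that ends a scan is a second case. At stake is how promptly the body overseeing all five sites gets an individual report of a serious event that arose during a study procedure. A site following the text could also reasonably disagree with another site about which route applies, because Section 15.2 uses the AE label for events it has excluded from that label.

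**Working it through.** No statistical figure is involved. The check is to classify each kind of event by the two attributes that the text uses and to read off its route to the Clinical Core.

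| Event | Meets the Section 15 criterion (distress ends the procedure)? | Serious? | Route to the Clinical Core |
|---|---|---|---|
| Claustrophobia ends a scan, no further harm | Yes | No | Monthly review (15.1) |
| Serious event that ends no study procedure | No | Yes | Individual report, five working days (15.2) |
| Serious event that stops a procedure for a medical reason, e.g. a seizure in the scanner | No | Yes | Individual report, five working days (15.2) |
| Serious event in which the subject's distress ends the procedure, e.g. an acute psychiatric crisis during the battery | Yes | Yes | Monthly review (15.1); no individual deadline stated |

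Only the last row is affected. It follows from three steps.

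1. The Section 15 criterion is met, because distress ended the procedure.
2. Section 15.2 covers only serious events that do not meet that criterion, so this event is outside it.
3. Section 15.1 is what remains, and it does not distinguish serious from non-serious AEs.

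Other parts of the protocol that might close the gap:

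- **Suicidality pathway (Sections 9.4, 12.1 and 12.2).** This gives a local response and notice to the Site PI. It sets no time for telling the Clinical Core.
- **Form completion (Section 14.1).** Electronic forms should generally be completed within 2 business days. A database entry is not an individual report that someone must act on.
- **IRB submission (Sections 6.9 and 15.2).** This runs in parallel, to a different body, with no deadline in the protocol.
- **Deviation reporting (Section 17.2).** This concerns the missed or incomplete procedure, not the seriousness of the event.

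On size, Table 5 lists at most 9 blood draws + 3 MRIs + 4 batteries = 16 procedure occasions per participant. With 50 participants that is at most 16 × 50 = 800 occasions on which such an event could arise. This is a ceiling on opportunity, not an expected count. The documents give no rate for serious distress events, and none is assumed here.

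**The case against.** The best defence is that Section 15 describes a tolerability class, since its examples are mostly mild and its wording is permissive. On that view Section 15.2 was meant to catch everything serious. That is probably the intent. It does not settle the matter, because the sentence excludes events that meet the criterion, and the criterion has no upper limit on severity.

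Three stronger readings are tempting, and the documents do not support them.

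- **That the order is inverted, so that any serious event stopping a procedure is on the slow track.** The criterion is distress that requires termination. A seizure, cardiac event or collapse that stops a scan for medical reasons does not meet it and stays under the five-working-day rule.
- **That affected events reach the Clinical Core about four times later.** Dividing a month by five working days (about 30/7 ≈ 4.3) compares the interval of a periodic review with the deadline for an individual report. Nothing says the Clinical Core first learns of an AE at the monthly review. It has QuesGen reports and dashboards under Section 17.2, and the Site PI's weekly notice is about as quick as five working days, though to a different recipient.
- **That there is no timely notice at all.** IRB submission runs alongside, and the single-IRB operating procedure cited in Section 6.9 is not among the documents at hand. It may contain prompt-reporting deadlines.

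It is also fair to say that a stopped procedure may surface as a deviation. For blood draws and processing, Section 17.2 says "deviations can proceed at the local level, but must be reported to the Clinical Core within 2 business days". A draw abandoned without a sample would plausibly come through that way. Incomplete scans and batteries are also listed as deviations, and in most instances these go to the Executive Committee before collection resumes for that subject at that time point. These routes reduce the chance that an event goes unnoticed, but none requires the serious event itself to be reported.

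**Conclusion.** The gap is real and narrow. As written, a serious event that also meets the distress-driven AE criterion is outside the protocol's only deadline for an individual report of a serious event to the Clinical Core. It is left to the weekly Site PI notice and the monthly review. No other section of the protocol supplies a deadline for that report.

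The conclusion rests on the literal wording of Sections 15 to 15.2 and on the absence of any other Clinical Core deadline in the protocol. It does not assume that the single-IRB procedure is silent, since that would concern a different recipient. The practical exposure is likely to be small: 50 participants, an observational design described as minimal risk, and anticipated AEs that are mostly mild. The point bears on safety oversight, not on the validity of the biomarker analyses. It is worth correcting because the contradiction sits in a stated rule and the correction is cheap.

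**What to change.** Reword the sentence in Section 15.2 along these lines: *Any serious event, whether or not it meets the AE criteria above, will be reported to the Clinical Core within five working days.* This reuses the protocol's own deadline and introduces no new one.

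Then make two consequential edits:

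- In Section 15.1, limit the weekly and monthly cycle to non-serious AEs. State that serious AEs still count toward the existing trigger for contacting a site when AEs exceed 10% of its enrolment, so that the change does not weaken that trigger.
- In Section 15.2, reconcile the label, so that events described as falling outside the AE criteria are not then called AEs.

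The cost is one sentence, two small edits, and a few more individual reports to the Clinical Core. No study procedure and no part of patient care changes.
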